## VAS - Scale

### - **Activity diary**

In order to record the patient's daily activities during the duration of the study, the patient will be asked to document their activities in the activity diary on a daily basis. The activity diary is given to the patient and instructed by the study management.

#### Objectification of everyday activities:

Activity diary

Objective parameters and their objectification:

### - **Force**

The maximum isometric force and the force development of the muscles supplied by the affected spinal nerve are tested in a standardized starting position. For this purpose, a dynamometer held by hand by the tester is used. The patient is asked to press against the examiner's hand as hard and as long as possible. In addition, a superficial electromyography is performed, in which the electrodes are glued to the points provided for this purpose on the skin. To ensure that the test situation remains isometric, the examiner applies exactly as much force as the patient is willing to deploy. The test is carried out 3 times in a row with a 30-second break. The values are transferred to the data sheet. The measurements take place on both sides, starting with the subjectively weaker side.

#### Objectification power:

The hand-held dynamometer (NOD, [www.to-nod.com](http://www.to-nod.com)) graphically and numerically records the strength and duration of the isometric power delivery. Superficial electromyography is performed with the PLUX EMG device ([www.biosignalsplux.com](http://www.biosignalsplux.com)) and evaluated with the associated software.

### - **Trunk mobility and trunk fluctuations**

#### **Mobility**

The maximum mobility of the spine is measured during forward bending (flexion), leaning backwards (extension) and tilting sideways to the left and right (lateral flexion) using the Sway Star™ system. The inspector makes sure that the pelvis remains fixed.

#### **Trunk swaying during 30 s - one-leg stand**

In order to record the ability to balance and the corresponding trunk reactions, the patient tries to stand as still as possible on one leg barefoot for 30 seconds. In this case, the patient stands to the side of the treatment table so that he or she can hold himself with his hand. The examiner stands behind the patient during testing. The fluctuations that occur during the balance test are measured using the Sway Star™ system. The measurements take place on both sides, starting with the subjectively weaker side.

#### **Hull Swaying during 8 m – Walking**

In order to measure the trunk movements during walking, the patient walks at a pace of 8 m. The trunk movements are recorded using the Sway Star™ system.

#### Objectification:

The fluctuations of the hull are recorded and evaluated with the Sway Star™ System ([www.b2i.info](http://www.b2i.info)). The Sway Star™ is a measuring instrument that contains gyroscopes. It is attached to a belt that is placed around the patient's waist. The data is evaluated with the associated Sway Star™ software and transferred to the data sheet.

### - **Sensors**

The sensory system of the affected area (segmentally associated dermatome) is tested directly on the skin in the radiation area. The results are transferred to the data sheet. The pain threshold is raised on a Valleix point along the iliac crest. Measurements are always taken at the same measuring points, on the affected side.

Objectification of sensor technology:

The pressure sensation is recorded by means of a monofilament, the 2-point discrimination with the Greulich star, the sense of vibration with the tuning fork (according to Rydel-Seiffer), the muscle reflex with the reflex hammer in a left/right comparison including acceleration measurement (accelerometer MSR165, [www.msr.ch](http://www.msr.ch)) and the pain threshold with the algometer (NOD, [www.to-nod.com](http://www.to-nod.com)).

- **Neurodynamics**

The neurodynamics of the affected spinal nerve are tested using the appropriate pain provocation test. For this purpose, a hydrogoniometer is required, with which the exact number of degrees at which the symptoms are triggered is measured. The number of degrees is transferred to the data sheet. The tests are carried out in a standardised manner. If the spinal nerve L2/L3 is affected, the crossed Lasègue test is performed, and for L4/L5/S1 the Lasègue test.

Objectification of neurodynamics:

Hydrogoniometer

- **Subcutaneous fat tissue and muscle fiber alignment**

The thickness of the subcutaneous fatty tissue is measured on the rectus femoris muscle, 10 cm above the patellar base, and on the medial gastrocnemius muscle at the level of the largest calf circumference, in both legs.

Objectification Thickness Subcutaneous Fat Tissue and Muscle Fiber Alignment:

The portable ultrasound device from Telemed ([www.pcultrasound.com](http://www.pcultrasound.com)) is used for this purpose. The images are evaluated with the Osirix ([www.osirix-viewer.com](http://www.osirix-viewer.com)) software and the number of millimetres, fat thickness and muscle fibre degree angle are transferred to the data sheet.

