**Overview of the measurement process**

Expiration	Data collection	Instrument	Time exposure
- Questionnaire	subjective health-related quality of life	SF-36 Questionnaire	5 min
- Questionnaire	subjective physical impairment	ODQ	5 min
- Pain Evaluation	subjective pain radiation and intensity	VAS	5 min
- Demography	Height, body weight, body fat percentage	Pain Drawings Stadiometer, Tanita – Scale	5 min
- Ultrasound measurement of the rectus femoris and gastrocnemius medialis muscles	Thickness of subcutaneous fatty tissue, alignment of muscle fibers, bilateral	Portable Ultrasound Machine (TeleMed)	10 min
- Trunk mobility	Mobility of the spine in flexion, extension, lateral flexion	Sway Star™	2 min
- Hull swaying	Torso movements during 30 s – one-leg stand, both sides	Sway Star™	2 min
- Hull swaying	Trunk Movement during 8m - Walking	Sway Star™	5 min
- Neurodynamics	Pain provocation test, bilateral	Hydrogoniometer	2 min
- Evaluation of the sensor technology	Sensation of pressure, 2-point discrimination, sense of vibration, muscle reflex, pain threshold bilateral	Monofilament, Greulich Star, Neurological Tuning Fork, Reflex Hammer, Accelerometer, NOD Algometer	10 min
- Force measurement	maximum isometric force, force development, bilateral	NOD – isometric load cell, surface electromyography	5 min

The maximum time required per measurement appointment is one hour. With 6 measurement points, the time required adds up to 6 hours and extends over 8 months.

In addition, the patient keeps an activity diary at home and logs the painkiller intake, which takes about 5 minutes a day.

The treating physiotherapist records the content of all therapy sessions. The protocol to be used for this purpose is explained and instructed to the physiotherapist by the investigators at the beginning of the study. The documentation of physiotherapeutic treatment is one of the duties of a physiotherapist, so there is no additional effort for him. All he has to do is use the protocol template. Furthermore, the treating physiotherapists are asked to continue their usual interventions and treatments regardless of the study participation of their patients.

The following biases could occur:

- Sociodemographic and personal characteristics of the subjects: men/women, age
- Duration of back pain
- Truthful keeping of the activity diary and painkiller intake log
- physiotherapeutic treatment

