By the time a patient presents to the neurosurgery department, the back pain has already reached a high degree of severity. The duration and intensity of symptoms vary and should be stratified in evaluation. The measurement times should be strictly adhered to in order to ensure comparability in time between the test subjects.

The study ends in the 8th month after the start of the study after the 6th and last measurement.

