## **4 STATISTICS AND METHODOLOGY**

### **4.1. Statistical analysis plan**

The required number of subjects was determined a priori with G\*Power (version 3.1.9.2; Franz Faul University of Kiel, Germany). The following design specifications were used: statistical test = Correlation Type of Power Analysis 'Computer required sample size – given  $\alpha$ , power and effect size'; tails = two; effect size = 0.5;  $\alpha$  = 0.05; power = 0.95. The target number of subjects was  $n$  = 42 based on these design specifications. The SPSS version 24 software is used for statistical data analysis (IBM, Armonk, NY, USA).

The data are first checked for normal distribution with the 'Shapiro-Wilk test'. The normally distributed data are analysed by means of parametric test procedures. Non-normally distributed data as well as non-metric data are checked with non-parametric tests. The correlations are recorded using the 'Pearson Correlation tests' and 'Spearman Correlation tests'.

Correlations between the subjective parameters (pain, physical impairment, activity diary), between the objective parameters (strength, balance, sensory, neurodynamics, muscle thickness

and physiotherapeutic objectives), as well as between the subjective and objective parameters are of interest and should be calculated.

The following working (H1) and null hypotheses (H0) are statistically proven or rejected:

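### Section 4.1 correlates neurodynamics without regard to which of two nerve-level-dependent tests produced the angle, so those correlations can be diluted or confounded

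*Combined protocol and SAP*

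**What the plan says.** The neurodynamics entry in section 2.2 of the combined protocol and SAP assigns the test by affected spinal nerve: "If the spinal nerve L2/L3 is affected, the crossed Lasègue test is performed", "and for L4/L5/S1 the Lasègue test". The recorded quantity is the same for both: "the exact number of degrees at which the symptoms are triggered is measured", and "The number of degrees is transferred to the data sheet". No separate variable per test is described. The measurement overview in section 3.3 lists this item as "Pain provocation test, bilateral".

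Section 4.1 asks for correlations "between the objective parameters (strength, balance, sensory, neurodynamics, muscle thickness" and physiotherapeutic objectives), and also between the subjective and the objective parameters. On method it says: "The correlations are recorded using the 'Pearson Correlation tests' and 'Spearman Correlation tests". It names no covariate.

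The only stratification mentioned is at the end of section 3.3: "The duration and intensity of symptoms vary and should be stratified in evaluation". Nerve level and test type are not among the factors. Section 3.1 does not restrict eligibility by nerve level, so both tests can occur in the sample.

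**The concern.** An angle from one provocation test and an angle from another share a unit but need not share a distribution. If they are entered as one variable, two things can happen.

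- **Dilution.** A shift in mean angle between tests adds variance that says nothing about the patient's status. A real within-test correlation then looks smaller.
- **Confounding.** Nerve level also decides which muscle's force is measured (section 2.2, Force) and which dermatome is tested (section 2.2, Sensors). For neurodynamics against force or sensory function, both variables can therefore shift with the same unmodelled factor. That can produce a correlation where none exists within a level, or mask one that does. Spearman does not remove this, because the ranks are taken across the mixed sample.

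At stake is the interpretation of the neurodynamics correlations that section 4.1 requires.

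**Working it through.** **The plan's own figure.** Inputs from section 4.1: r = 0.5, two-sided alpha 0.05, power 0.95, n = 42. With a noncentral t, ncp = sqrt(n r²/(1 − r²)) = sqrt(42 × 0.25/0.75) = 3.74 and df = 40, power is 0.9545, and 42 is the smallest n that reaches 0.95. The figure reproduces and is not disputed. For two continuous, normally distributed variables, power at n = 42 is 0.934 by simulation and 0.929 by Fisher z. These are the baselines below.

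**Dilution.** Let p be the share of patients given the L2/L3 test and d the difference in mean angle between the tests, in within-test SDs. The documents give neither, so both are assumptions. If the partner variable is unrelated to level, the variance of the pooled angle is inflated by 1 + p(1 − p)d², and

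pooled r = 0.5 / sqrt(1 + p(1 − p)d²).

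For example, p = 0.20 and d = 2 give 0.5 / sqrt(1 + 0.16 × 4) = 0.5 / 1.281 = 0.390. Fisher-z power is Φ(atanh(r) × sqrt(39) − 1.96). Simulated power uses 40,000 runs per scenario.

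| p | d | pooled r | power, simulated | power, Fisher z |
|---|---|---|---|---|
| any | 0 | 0.500 | 0.93 | 0.93 |
| 0.05 | 0.5 | 0.497 | 0.93 | 0.93 |
| 0.10 | 1 | 0.479 | 0.91 | 0.90 |
| 0.20 | 1 | 0.464 | 0.89 | 0.88 |
| 0.20 | 2 | 0.390 | 0.74 | 0.73 |
| 0.30 | 2 | 0.369 | 0.69 | 0.68 |
| 0.50 | 2 | 0.354 | 0.65 | 0.64 |

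**Confounding.** Now let the true within-level correlation be 0 and let the partner variable shift by e SDs between levels. With v = p(1 − p),

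spurious r = v d e / sqrt((1 + v d²)(1 + v e²)).

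| p | d | e | spurious r | rejection rate at n = 42 (nominal 0.05) |
|---|---|---|---|---|
| 0.10 | 1 | 0.5 | 0.04 | 0.059 |
| 0.20 | 1 | 1 | 0.14 | 0.14 |
| 0.30 | 2 | 1 | 0.28 | 0.44 |

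With d = 0 the simulated rejection rate stays at about 0.05 even when e = 1.

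**Cost of adjusting.** A partial correlation with one covariate loses one degree of freedom. On the noncentral-t basis that reproduces 42, power for a within-test r of 0.5 is 0.950 at n = 42, against 0.9545 unadjusted, and it returns to 0.9545 at n = 43.

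**The case against.** The best defence is that the plan nowhere says the two sets of degrees will be merged. Neurodynamics in section 4.1 may be only a heading. In the same list, sensory function covers five measurements on different instruments, and balance covers more than one SwayStar task. This stands in part: pooling is the plain reading, but it is inferred from silence. The supportable complaint is that the plan does not say how two tests become one analysable variable.

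Second, the harm depends on quantities the documents do not report. This stands in full. With few L2/L3 patients or similar angle distributions the effect is negligible. The formula is for Pearson with a partner unrelated to level. If the partner does vary by level, the pooled coefficient can move either way.

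Third, none of the H0/H1 pairs in sections 2.1 and 4.1 involves neurodynamics. This also stands, and it limits the importance. It does not remove the point: section 2.2 lists neurodynamics among the objective parameters of the primary objective, and section 4.1 says its correlations should be calculated.

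A reader might infer that these correlations are in fact diluted or spurious, or that the sample size or the listed hypotheses are undermined. The documents support neither. They give no angle data, and the calculation of n = 42 is not tied to neurodynamics.

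**Conclusion.** The point holds in conditional form. As written, the plan lets angles from two level-dependent tests enter one plain correlation, and nothing separates or adjusts for test. The resulting coefficients can be diluted if the angle distributions differ. They can be confounded where the partner also depends on nerve level, as force and sensory testing do by design.

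Under the assumed ranges, a within-test r of 0.50 appears as anything from 0.497 to 0.354, with simulated power at n = 42 from 0.93 down to 0.65. Through a mean shift there is no effect at d = 0. Both p and d are assumptions.

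Only the general correlations in section 4.1 are touched. This is a worthwhile clarification and not a threat to the study's stated hypotheses.

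**What to change.** Record on the data sheet which provocation test was used for each patient. In section 4.1, state that correlations involving neurodynamics are partial correlations (Pearson or rank-based) adjusted for test type. The cost is one data field, one sentence and one degree of freedom, which is about one patient at the planned size. The adjustment removes a mean shift between tests; it does not equalise their spread.

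Two alternatives are weaker:

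- **Separate significance tests within each test type.** If 20% of patients have the L2/L3 test, that stratum holds about 8 of 42. Fisher-z power for r = 0.5 is then Φ(0.549 × sqrt(5) − 1.96) = 0.23.
- **The affected-minus-unaffected difference.** It has no value when no symptoms are triggered on the unaffected side, and patients without radiculopathy may have no affected side.

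The same sentence should say which side's angle is analysed, since the test is bilateral. The sponsor should also state how eligible patients without an affected spinal nerve are handled in this analysis, because section 2.2 names no test for them. Which test is used at which nerve level is a clinical matter and is left as it is.

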## 2.3 Project design

The study is a prospective observational study. There is no intervention. No influence is exerted on the normal physiotherapeutic and medical treatment of patients. At the Graubünden Cantonal Hospital in Chur, repeated measurements are being carried out. Therefore, a single-center study is available here.

## 3 PROJECT POPULATION AND STUDY PROCEDURES

### 3.1 Project population, inclusion and exclusion criteria

Participants will be recruited by [name]. The study will include people who suffer from back pain, with or without radiculopathy, and who present themselves to the neurosurgery department at the Graubünden Cantonal Hospital in Chur. Included are those patients who speak and write German, who will go to physiotherapy treatment because of their back problems and are willing to record their daily activities and intake of pain medication in a diary at home. Excluded are patients who do not suffer from back pain, with or without radiculopathy, or who do not attend physiotherapy treatment due to their back problems, or who are not willing to keep an activity diary with a log of painkiller intake at home.

The German language must be understood orally and in writing in order to understand the patient information and sign the informed consent form. Patients will be definitively included if they meet the inclusion criteria and have signed the informed consent form for participation in the study.

Inclusion and exclusion criteria are summarized in the table below. All inclusion criteria must be met in order to participate in the study. In the case of the exclusion criteria, one unfulfilled point is sufficient to be excluded.

#### Overview of inclusion and exclusion criteria

Inclusion Criteria	Exclusion criteria

- Back problems with / without radiculopathy

- Understanding of German orally and in writing

- Physiotherapeutic treatment for back pain

- Willingness to keep an activity diary, including a protocol for taking painkillers

	

- No back problems with / without radiculopathy

- No understanding of German orally or in writing

- No physiotherapy treatment due to back pain

- No willingness to keep an activity diary and/or log of painkiller intake

### 3.2 Recruitment, screening and informed consent procedure

After approval of the study protocol by the Cantonal Ethics Committee Zurich, the recruitment of suitable subjects is to begin from October 2018 to December 2020. The data collection will take place continuously from October 2018 until June 2021 (see Chapter 3.3).

When the patient with back problems, with or without radiculopathy, is presented to the neurosurgery department at the Graubünden Cantonal Hospital in Chur, he or she is informed that the study is taking place. Both conservative and surgical patients are included. If the patient wants to participate in the study, he or she will be given the written study information, which he or she should read through at his leisure. If you have any questions, you can contact the director of studies at any time. Once all questions have been clarified and the patient is willing to participate in the study, he or she signs the study information and the declaration of consent. Once the signed study information and signed declaration of consent have been submitted by the study management, the health questionnaire is filled out together with the patient, which checks the inclusion and exclusion criteria. If the patient meets the inclusion criteria, the measurement points are planned by the examiner.

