### 3.3 Study procedures

After oral study information by [name], after signing the written study information and declaration of consent and clarifying the inclusion and exclusion criteria (health questionnaire), the measurement points are planned. A total of 6 measurement points are determined. The first 5 appointments take place once a month, followed by a 3-month measurement-free period, after which the last and 6th measurement takes place. In the event of complications or worsening symptoms, the head of the study, who is also the attending physician, is informed immediately.

If a conservatively treated patient needs surgery during the study (e.g. due to a worsening of his symptoms), the preoperative data set will be recorded and a new postoperative data set will be opened, provided that the patient wishes to continue participating and/or is not excluded by the study management. The study includes conservatively treated (physiotherapy) and surgically treated patients equally.

If imaging techniques are used in the context of medical diagnosis, these images are included in the data collection and taken into account as far as possible in the interpretation of the data.

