## 4.2. Handling of missing data

Since statistical values of the individual relationships are determined, the data is also included if a test subject does not participate in all measurement points and/or measurements. Incomplete data from individual assessments (aborted tests) are not included in the final data analysis, but are recorded and stored.

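### Section 3.2 ends data collection in June 2021, one month too early for a patient first measured in December 2020 to reach the sixth measurement

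*Combined protocol and SAP*

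**What the plan says.** All the relevant text is in the combined protocol and SAP.

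- **Recruitment window (Section 3.2):** "the recruitment of suitable subjects is to begin from October 2018 to December 2020".
- **Data-collection window (Section 3.2):** "The data collection will take place continuously from October 2018 until June 2021". This sentence refers the reader to Chapter 3.3, so the dates and the visit schedule are meant to agree.
- **Schedule (Section 3.3):** "A total of 6 measurement points are determined", and "The first 5 appointments take place once a month, followed by a 3-month measurement-free period, after which the last and 6th measurement takes place".
- **Length of the series (Section 3.3, overview of the measurement process):** "With 6 measurement points, the time required adds up to 6 hours and extends over 8 months", and shortly afterwards "The study ends in the 8th month after the start of the study after the 6th and last measurement".
- **Timing discipline (same place):** "The measurement times should be strictly adhered to in order to ensure comparability in time between the test subjects". No visit window is given.
- **Missed visits (Section 4.2):** "the data is also included if a test subject does not participate in all measurement points and/or measurements".

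The documents give no shortened series for late recruits and no extension beyond June 2021. They also do not say whether recruitment closes early once the target of 42 in Section 4.1 is reached.

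**The concern.** Between the last permitted recruitment month (December 2020) and the last month of data collection (June 2021) there are six months. The series needs seven. A patient enrolled in the final recruitment month therefore cannot complete the schedule that Section 3.3 prescribes.

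The visit at risk is the sixth. It is the only observation after the three-month gap, and Section 1 says the study wants to follow the parameters over time. For a December 2020 recruit the site would have to do one of three things: leave the sixth measurement out, bring it forward against the instruction to keep strictly to the measurement times, or continue past the stated end of data collection. The plan provides for none of these. The gap can be seen in advance and depends only on the enrolment date.

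**Working it through.** **Inputs.** Recruitment runs from October 2018 to December 2020 (Section 3.2). Data collection runs until June 2021, taken at its most generous as 30 June 2021 (Section 3.2). There are six measurements: five at monthly intervals and the sixth after a three-month gap (Section 3.3). The target is 42 patients (Section 4.1). I assume the first measurement takes place on the day of recruitment, which favours the plan. Consent, the health questionnaire and appointment planning come before it, so any delay makes the fit worse.

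**Step 1: length of the series.** Five monthly visits span 4 intervals, so they fall at months 0, 1, 2, 3 and 4. The sixth falls at 4 + 3 = month 7. Counting the month of the first visit as month 1, this is the 8th month, which agrees with the statement in Section 3.3 that the study ends in the 8th month.

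**Step 2: try to reproduce June 2021.** Date of measurement 6 = date of measurement 1 + 7 months.

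| First measurement | Measurement 5 (+4 months) | Measurement 6 (+7 months) | By 30 June 2021? |
|---|---|---|---|
| 30 November 2020 | 30 March 2021 | 30 June 2021 | yes |
| 1 December 2020 | 1 April 2021 | 1 July 2021 | no |
| 31 December 2020 | 30 April 2021 | 31 July 2021 | no |

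June 2021 is reproduced only if first measurements stop on 30 November 2020. Every December 2020 start falls outside. Measurement 5 is never affected.

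**Step 3: other readings of the schedule.**

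- *8 elapsed months* (a literal reading of the stated span): 31 October 2020 + 8 months = 30 June 2021, which fits; 1 November 2020 + 8 months = 1 July 2021, which does not. The latest sixth measurement is 31 August 2021.
- *Each month read as 4 weeks* (7 × 4 = 28 weeks, the most lenient): a 15 December 2020 start ends on 29 June 2021, but starts from 17 December 2020 onward still end after 30 June.

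The mismatch survives all three readings; only its width changes.

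**Step 4: size.** The recruitment window is 92 + 365 + 366 = 823 days (October to December 2018, then 2019, then 2020), or 27 calendar months. Assuming uniform accrual of 42 patients:

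| Reading | Late recruitment days | Share of 823 days | Patients expected to miss measurement 6 |
|---|---|---|---|
| 7 months | 31 | 3.8% | 42 × 31/823 = 1.6 |
| 8 elapsed months | 31 + 30 = 61 | 7.4% | 42 × 61/823 = 3.1 |
| 28 weeks | 15 | 1.8% | 42 × 15/823 = 0.8 |

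Counting by months gives the same result: 42/27 = 1.56 patients per month, for one or two affected months.

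**The case against.** The strongest reply is that this hardly matters. December 2020 is the outer edge of the window, and if 42 patients are enrolled sooner nobody is affected. Even with recruitment to the last day, one or two patients would lose one visit of six, and Section 4.2 keeps everything else they contribute. All of that stands, and it is why the point is minor. It does not make the calendar feasible, though. Section 4.2 tolerates a missed visit; it does not make room for one the plan itself schedules after closure.

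A second reply is that the 7 and 8 months in Section 3.3 are one schedule counted in two ways. This also largely stands. Ending in the 8th month is what 7 elapsed months gives, and a span of 8 months can be counted with both end months included. A reader might infer that the sixth measurement falls in August 2021 and that November recruits are lost too. The documents do not require that reading, so it serves here only as an upper bound.

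Two further inferences are tempting. One is that power at the sixth measurement is compromised. Section 4.1 sizes the study for a single correlation without naming a time point, and none of the listed hypotheses is tied to the sixth measurement, so there is no planned power at that visit to lose. The other is that late recruitment might bunch and make the loss substantial. Nothing in the documents suggests such bunching.

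**Conclusion.** The point holds as a minor inconsistency. With recruitment allowed to the end of December 2020 and a seven-month series, the last sixth measurement falls on 31 July 2021, one month after data collection is stated to end. Any patient first measured in December 2020 would be affected, at that visit only.

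The expected loss is about 1.6 of 42 patients (4%), with a range of 0.8 to 3.1 across the readings of the schedule. This rests on two assumptions the documents do not state: uniform accrual over the whole window, and a first measurement on the day of recruitment. The calendar conflict itself does not depend on the accrual assumption.

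A reader might infer that the last recruits will certainly lose the sixth measurement. The documents support only that they would if enrolment actually continues into December 2020 and data collection stops as stated. One question is open: Sections 3.3 and 3.4 start a new postoperative data set when a conservatively treated patient goes on to surgery, without saying whether the six-visit series restarts. If it does, some patients enrolled earlier could also run past June 2021.

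**What to change.** In Section 3.2, make one of these changes:

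- extend the end of data collection to at least 31 July 2021; or
- set 30 November 2020 as the last date for a first measurement.

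If 8 elapsed months are intended, use 31 August 2021 or 31 October 2020 instead. State the timing of the sixth measurement in Section 3.3 as elapsed months from the first, so that it is clear which pair of dates applies.

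Either change alters one date. Extending costs one further month of appointments (two under the 8-month reading) for the few patients concerned, and adds no visits beyond those already planned. Closing enrolment a month early means recruiting 42 patients in 26 months rather than 27, or 42/26 = 1.62 per month instead of 1.56. Extending is the simpler choice because it leaves the recruitment plan alone.
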